10.11. Clean Room Committee

In studies of existing data, decisions about study design or analysis should not be informed by knowledge of how such decisions might affect study results. The study team has attempted to pre-specify all statistical analysis plans to a sufficient degree of detail that ambiguity about how the results will be obtained is minimized. However, often data will need to be examined to inform key aspects of the study design or analysis, and in other cases, issues discovered during analysis might require certain deviations from the planned design and/or analysis.
To avoid biasing point estimates and standard errors for the primary comparative analysis, the individuals making these decisions will be isolated from knowledge about how these decisions might affect outcomes. To do this, the 3 individuals will be designated to be members of the CRC, and this designation will be recorded in the study log. Analysts will have direct access to the data and will build all analytic files and implement all data analysis. Study team members not designated as CRC members will work with the analysts to review and understand output tables.

Members of the CRC will make all decisions about the conduct of these studies, including decisions about protocol deviations as well as the reporting and interpretation of results in reports. Additionally, based on data supplied to them by the analysts, the CRC will make decisions about changes in analytic approaches, model specification, group inclusion/exclusion criteria, and variable definitions. The data supplied by the analyst should not provide any direct information about how such protocol changes might affect results. To accomplish this, preliminary results that contain outcome statistics summarized by group (OCA-treated versus not OCA-treated) will not be presented to the Investigators. If, for some reason, results need to be presented by group, the group will be masked by the analysts. All aspects of this process will be tracked, specifically:

- All requests for interim data or results will be entered into the study log where they can be viewed by all study team members.
- All protocol deviations will be logged along with the rationale for the change. Protocol changes will not be made unless all Investigators agree to the change.
- Minutes of meetings in which decisions about protocol changes are made will be saved.
- The original protocol as well as all modified versions will be accessible to all Investigators and analysts.

The original protocol and the study log will be made available as appendix material for all reports and publications.

11. DIRECT ACCESS TO SOURCE DATA/DOCUMENTS

The data in these studies are de-identified. The Komodo Health data use agreements and the Global PBC registry Institutional Review Board (IRB) approval specify that these data may not be re-identified. In addition, the Global PBC registry site agreements do not allow for the transfer of data outside of the Global PBC registry.

The Clinical Research Organization (CRO) will ensure the Investigator's understanding of all applicable regulations and standard operating procedures (SOPs) and will ensure an understanding of the protocol and maintenance of all requisite documentation. The CRO will have full access to the Komodo Health data and analyses to be able to ensure these studies are conducted per protocol. The CRO can also review data and programming on site with a member of the Global PBC Study Group.

A Study Data Tabulation Model (SDTM) dataset will be provided to the FDA for the Komodo Health dataset. Should the FDA have questions or queries, a member of the Global PBC Study

Group will make themselves available on site at the FDA with a laptop computer containing the Global PBC registry analytic dataset and can both review data and run queries as required by the FDA.

12. QUALITY CONTROL AND QUALITY ASSURANCE

In 2021, the FDA released 4 draft guidance documents defining data quality, management, and analyses of real-world data, including guidance specific to claims data and disease registries. Given the extensive documentation requirements, separate supplemental protocols will be submitted, one for the Global PBC registry and one for the Komodo Health dataset.

12.1. Data Collection and Transfer

12.1.1. Komodo Health

Komodo Health merges administrative claims across >350 health plans including commercial (63%); Medicaid (23%); Medicare (10%); dual eligible (<1%); and other (2%). The dataset represents more than 325 million unique patients in the US between June 2015 and July 2021. The datasets include all inpatient, outpatient, and procedure claims, as well as service dates, associated ICD-9 and ICD-10 codes, and provider data.

Data from each payer are tokenized, deidentified, and encrypted by the individual payer (see Section 12.2.2). Some examples of file formats Komodo Health intakes from sources include TXT, CSV, and DAT file types. Komodo Health commonly receives data as (but not limited to) comma-delimited, pipe-delimited, and tab-delimited files. A transit token specific to the payer and Komodo Health is used, and once received the data are de-encrypted, including a final patient token. Thirty-six percent of plans transfer their data through a Komodo Health secure FTP site; 64% of plans provide a secure FTP site to Komodo Health to retrieve the data. Komodo Health receives and stores data in AWS S3 buckets.

Plans provide uncurated (raw) data. Data cleaning, such as deduplication, will be specified in the supplemental submission. Cleaned data are merged and linked via token, thus patients are able to be followed longitudinally across plans that contribute data. After Komodo Health finishes processing the data, they are made available as a Snowflake database in the Sentinel cloud environment.

12.1.2. Global PBC Registry

Data for the Global PBC registry is collected through the CASTOR trial platform. The CASTOR System, which has been employed for registrational trials, includes eCRFs, cloudbased data collection, and download of data in SAS format for analysis. The data are only transferred to the University Health Network system, with no additional data transfer, and are analyzed in the SAS environment. The eCRF prevents the input of test values outside of medically plausible range and the input of duplicate data. Source data cannot be modified. The Global PBC registry protocol, eCRFs, and all data cleaning and transformations of variables included in this analysis will be specified in the supplemental submission.

12.1.3. National Death Index

The NDI is a central computerized index of death record information on file in state vital statistics offices. The Centers for Disease Control and Prevention and the National Center for Health Statistics compile deaths annually from computer files submitted by state vital statistics offices. Numerous studies have confirmed the validity of the NDI. The NDI has previously been linked to the Komodo Health database (see Section 12.3) and the datafile will be kept firewalled from analysts until the CRC authorizes unblinding. The NDI will be used to ascertain death as part of the composite endpoint.

The Komodo Health data contains information on hospital discharge status, including death at discharge. Death status, combined with a lack of addition claims >30 days after deaths will be compared to the NDI database. If a death on hospital discharge (plus lack of additional claims) is observed in the Komodo database but not in the NDI database, it will be included as a primary endpoint.

12.1.4. Quest Diagnostics

Quest Diagnostics has >2000 testing facilities with specimens processed at 26 central laboratories in the US (excluding those devoted exclusively to clinical trials). Specimen collection and testing protocols are standardized nationally. Date of test, laboratory value results, normal range limits, and associated ICD-10 codes are entered at each lab facility. Data are sent electronically to the testing site, and also to a centralized main frame and entered into the national database within 7 days. Specifications on data storage, transfer, and cleaning will be included in a supplemental submission.

These studies will utilize ALP, TB, ALT, AST, and platelets to propensity weight treated and untreated patients at index, and to determine UDCA treatment failure. AMA data will be used to validate the ICD-10 PBC claims diagnostic criteria.

12.1.5. LabCorp

LabCorp has >2100 testing facilities with specimens processed at 15 primary laboratories in the US (excluding specialty testing facilities such as oncology and genetic testing). Specimen collection and testing protocols are standardized nationally. Date of test, lab value results, normal range limits, and associated ICD-10 codes are entered at each lab facility. Data are sent electronically to the testing site, and also to a centralized main frame and entered into the national database. Specifications on data storage, transfer, and cleaning will be included in a supplemental submission.

These studies will utilize ALP, TB, ALT, AST, and platelets to propensity weight treated and untreated patients at index, and to determine UDCA treatment failure. AMA data will be used to validate the ICD-10 PBC claims diagnostic criteria.

12.1.6. OPTN Transplant Registry

OPTN collects and reports data on every US organ donor, transplant candidate, recipient, and outcome. Data are collected through a standardized eCRF using the online UNet database system. Specifications on data storage, transfer, and cleaning will be included in a supplemental submission.

The OPTN registry will be the primary data source to ascertain liver transplant as part of the composite endpoint. The Komodo Health data contains information on hospital admissions, including codes for liver transplant (see Appendix A). Hospitalization for liver transplant in Komodo Health claims will be compared to the OPTN database. If a liver transplant is recorded on hospital discharge but not in the OPTN database, it will be included as a primary endpoint.

12.2. Data De-identification

12.2.1. Global PBC Registry

The data collected at each site are de-identified by removing all identifying data fields (name, address, date of birth, etc.) prior to being sent to the Central Coordinating Site. A unique Global PBC Study Group study number is assigned to each site and each participant within the site and does not utilize identifying information in creating the patient number. Identifiers and their relation to the Global PBC Study Group number are maintained only at the study site and not by the central Data Coordinating Site.

12.2.2. Komodo Health

Datavant's de-identification engine is designed for use on structured healthcare data. The de-identification program performs 2 functions: de-identification of the data set through removal or modification of identifying data, and the insertion of encrypted patient tokens. De-identification includes the following:

- Zip Code: Reduced to the initial three characters to define a zip area. Based on the Health Insurance Portability and Accountability Act (HIPAA) rules, however, even three-digit zip areas with a combined population of less than 20,000 are either nulled out or are combined again with additional zip zones to ensure that populations exceed this minimum.
- Date of Service: Dates of service (eg, admission dates, discharge dates, prescription fill dates, and procedure dates) are typically preserved when using a statistical de-identification methodology.
- Date of Birth: Converts all birth dates to birth year. All dates of birth where the individual aged ≥89 years as of the date of de-identification would be modified to reflect an age of 89.
- Medical Records Numbers: Removed where present
- Telephone Numbers: Removed where present
- Email Address: Removed where present
- Social Security Numbers: Removed where present
- Beneficiary Numbers: Removed where present
- Vehicle Information: Removed where present
- Device Identifiers and Serial Numbers: Removed where present
- URL Addresses: Removed where present

- IP Addresses: Removed where present
- Biometric Values: Removed where present in claims data; retained in Quest Diagnostics and LabCorp
- Image Fields: Removed as defined by the data source

Datavant does not perform de-identification and tokenization itself and does not have access to the user's system or identifying information. The de-identification process is executed by the institution that owns the data, ie, Datavant's technology is installed and run locally behind the users' firewalls.

12.3. Data Linkages

Two sets of linkages are relevant for Komodo Health: initial link of contributing administrative claims databases; and linkage of laboratory data (LabCorp and Quest Diagnostics), death date (NDI), and transplant date (OPTN registry). All data linkages will be done through Datavant tokenization.

Across all datasets, as the Datavant program de-identifies a patient record, it also generates one or more tokens for that record. Tokens are based on the personally identifying data in the record, but the token itself does not incorporate this information in the identifier. The tokens are consistently created from any data set where the underlying identifying information is the same. Matching tokens are used to link a patient's record in one data set with a record for the same patient in a different set, without exposing the identifying information of that patient. Matching can be deterministic (eg, based on social security number) or probabilistic (eg, based on combination or name, sex, birthdate, 3-digit zip code, etc).

The tokens used to link records in de-identified data sets cannot be reversed to reveal the patient's identifying information. The first step of the token creation process is the use of an irreversible hash function, which ensures that the patient's personally identifying information used to create the token cannot be recovered from the output value. In the second step of the process, the hash value (ie, "Master Token") is encrypted with a site-specific encryption key to generate the final encrypted patient token. While the same patient information will always create the same Master Token, site-specific encryption means that a single patient will have a unique token (ie, a "site-specific token") in each specific user's data set. Site-specific encryption ensures that a breach at one data site will never compromise the tokens or protected health information at any other data site. Datavant's QA testing protocols and results will be included in the supplementary submission.

Across all datasets, Datavant will create 2 tokens based on:

- Last name + first name + gender + date of birth
- Last name (soundex) + first name (soundex) + gender + date of birth

In the event this produces 2 patients with one token (called a "collision") or one patient with 2 tokens, Datavant will then match on social security number and/or address (when available in the dataset). In the overall Komodo Health claims database, in the match with the NDI, and in the match with Quest Diagnostics data, this has produced 99% exact match. In the subset of

PBC patients, only 873 of 164,942 patients are flagged as a collision and have been removed from analysis. The same process will be used with the OPTN transplant data.

12.4. Data Harmonization

The Global PBC registry collects data via a standardized eCRF. As such, data harmonization across data sources is not required.

The Komodo Health database merges administrative claims data from multiple insurers in the US. Claims are then merged with NDI for date of death; LabCorp and Quest Diagnostics databases for laboratory tests and values; and OPTN transplant registry for date of liver transplant. Below are the data sources and variables for which data harmonization is required and performed.

12.4.1. Komodo Health and National Death Index

The primary endpoint is a composite of all-cause death, liver transplant, and hospitalization for hepatic decompensation. The primary source for death will be the NDI. The Komodo Health claims database contains hospital discharge status, including "death." Hospital discharge of death will be compared to the NDI. Should a death be recorded on hospital discharge but not in the NDI, and if the patient has no healthcare claims 30 days after the "death" discharge, the patient will be coded as a death using the hospital discharge date.

12.4.2. Komodo Health and OPTN Liver Transplant

The primary endpoint is a composite of all-cause death, liver transplant, and hospitalization for hepatic decompensation. The primary source for liver transplant will be the OPTN transplant registry. Hospitalization for liver transplant in Komodo Health claims also will be ascertained through inpatient ICD-10 codes (see Section 12.4.3 and Appendix A). Komodo Health liver transplant claims will be compared to the OPTN database. Should a liver transplant be recorded for a hospitalization but not in the OPTN database, it will be included as a primary endpoint.

12.4.3. Komodo Health Hospitalization for Hepatic Decompensation

The primary endpoint is a composite of all-cause death, liver transplant, and hospitalization for hepatic decompensation. The primary source for hospitalization for hepatic decompensation will be Komodo Health claims. The definition will include inpatient admission ICD-10 codes that appear in any position, and includes:

- Variceal bleed: ICD-10: I85.01, I85.11, I86.4 and ICD-9: 456.1, 456.21, 456.8
- Ascites: ICD-10: K70.11, K70.31, K71.51, R18.0, R18.8, J94.8, K65.2 and ICD-9: 567.23, 571.2, 789.51,789.59, 511.8, 567.23
- Hepatic encephalopathy: ICD-10: B15.0, B16.0, B16.2, B17.11, B19.0, B19.11, B19.21, K70.41, K72.11, K72.90, K72.91 and ICD-9: 572.2, 070.0, 070.20, 070.41, 070.6, 070.71; or utilization of lactulose and/or rifaximin

As ICD-10 codes are standard across the US healthcare industry, there is no need for further harmonization across contributing health plans.

12.4.4. Quest Diagnostics and LabCorp

Within each laboratory provider, sample collection, test, and normal ranges are standardized. Collection and transport specifications, laboratory method, and normal ranges for each test are provided by each lab below.

- Total bilirubin (test code: Quest 285, LabCorp 001099)
 - Quest Diagnostics: Samples are collected in sodium heparin (green-top) or lithium heparin (green-top) tubes, spun in a serum separator tube, transported in a serum separator tube wrapped in foil or transferred to an amber transport vial, and stored/transported at room temperature with stability up to 24 hours. Spectrophotometry is performed on 1 mL serum. ULN is 1.2 mg/dL.
 - LabCorp: Samples are collected in red top gel-barrier tube or lithium heparin (green-top) tubes, with serum separation in ≤45 minutes, and stored/transported at room temperature with stability up to 3 days. Spectrophotometry testing is performed on 1 mL serum. ULN is 1.2 mg/dL for ≥18-year-olds.
- Alkaline phosphatase (test code: Quest 234, LabCorp 001107)
 - Quest Diagnostics: Samples are collected in sodium heparin (green-top) or lithium heparin (green-top) tubes, spun and transported in a serum separator tube, and stored/transported at room temperature with stability up to 7 days. Spectrophotometry is performed on 1 mL serum. ULN in U/L for 18- to 19-year-olds is 169 for men and 128 for women; for 20- to 49-year-olds is 130 for men and 125 for women; and for ≥50-year-olds 144 for men and 153 for women.
 - LabCorp: Samples are collected in red top gel-barrier tube or lithium heparin (green-top) tubes, with serum separation in ≤45 minutes, and 1 mL serum transported in plastic separator tube, and stored/transported at room temperature with stability up to 14 days. Kinetic testing is performed on 1 mL serum. ULN in IU/L for 18- to 20-year-olds is 125 for men and 106 for women; for ≥21-year-olds is 121 for men and women.
- Alanine aminotransferase (test code: Quest 823, LabCorp 001545)
 - Quest: Samples are collected in sodium heparin (green-top) or lithium heparin (green-top) tubes, spun and transported in a serum separator tube, and stored/transported at room temperature with stability up to 72 hours. Spectrophotometry is performed on 1 mL serum. ULN in U/L for 18- to 19-year-olds is 46 for men and 32 for women; for ≥20-year-olds is 46 for men and 29 for women.
 - LabCorp: Samples are collected in red top gel-barrier tube or lithium heparin (green-top) tubes, with serum separation in ≤45 minutes, and stored/transported at room temperature with stability up to 7 days. Kinetic testing is performed on 1 mL serum. ULN is 44 IU/L for ≥18-year-olds.

- Aspartate Aminotransferase (test code: Quest 822, LabCorp 001123)
 - Quest Diagnostics: Samples are collected in sodium heparin (green-top) or lithium heparin (green-top) tubes, spun and transported in a serum separator tube, and stored/transported at room temperature with stability up to 4 days.
 Spectrophotometry is performed on 1 mL serum. ULN in U/L for 18- to 19-year-old men and women is 32; for men, 20- to 49-year-olds is 40 and 250-year-olds is 35; for women, 20- to 44-year olds is 30 and 245-year-olds is 35.
 - LabCorp: Samples are collected in red top gel-barrier tube or lithium heparin (green-top) tubes, with serum separation in ≤45 minutes, and stored/transported at room temperature with stability up to 7 days. Kinetic testing is performed on 1 mL serum. ULN is 40 IU/L for ≥18-year-olds.
- Platelets (test code: Quest 723, LabCorp 005249)
 - Quest Diagnostics: Samples are collected in lavender-top (EDTA) tubes and stored/transported at room temperature with stability up to 48 hours. Testing is performed on 0.5 mL whole blood using an automated cell counter. Lower limit of normal (LLN) is 150,000 per uL for ≥18-year-olds.
 - LabCorp: Samples are collected in lavender-top (EDTA) tubes, immediately inverted 8 to 10 times, and stored/transported at room temperature with stability up to 1 day. Testing is performed on 0.5 mL whole blood using an automated cell counter. LLN is 150,000 per uL for ≥18-year-olds.

12.4.5. Cirrhosis

In the Global PBC registry, cirrhosis is assessed as positive for one or more of the following criteria:

- Biopsy Stage 4;
- Transient elastography ≥ 16.9 kPa;
- Radiological evidence (nodular liver or enlargement of portal vein + splenomegaly);
- Clinical features of portal hypertension defined as platelet count <140 000/mm³ with: persistent decrease in serum albumin; or, TB >2x ULN; or prothrombin time/INR > ULN (not due to antithrombotic use)

In the Komodo Health database, imaging data are not available and measures such as INR are not consistently collected. The Sponsor created and validated an algorithm for a claims-based cirrhosis diagnosis, defined as: cirrhosis ICD-10 (K74.5; K74.60; K74.69) with liver imaging and/or biopsy in 6 months preceding diagnosis (for imaging codes see Appendix A). Prevalence estimates in patients with PBC based on these codes in the HealthCore and Optum databases, stratified by decompensation and portal hypertension, were compared to data from the Global PBC registry (Table 2). As shown, the concordance was high. Additional analyses examining the association between these groups and clinical outcomes (death, liver transplant and hepatic decompensation) demonstrated that the expected relationships, with cirrhosis in the presence of portal hypertension or decompensation significantly increasing risk of death, liver failure and liver transplantation (Figure 3).

Table 2:Comparison of Imaging-based (Global PBC) and Claims-based (HealthCore,
Optum) Prevalence of Cirrhosis in PBC Patients.

	Global PBC	Optum	HealthCore
PBC	N=2,982 (100%)	N=4,328 (100%)	N=4,348 (100%)
Compensated non-cirrhosis	N=2,275 (76.3%)	N=3,303 (76.3%)	N=3,317 (76.3%)
Compensated cirrhosis, without portal hypertension	N=314 (10.5%)	N=271 (6.3%)	N=225 (5.2%)
Compensated cirrhosis, with portal hypertension	N=105 (3.5%)	N= 276 (6.4%)	N=295 (6.8%)
Decompensated	N=283 (9.5%)	N=478 (11.0%)	N=511 (11.8%)

Figure 3: Incidence Rates for Major Hepatic Events Stratified by Cirrhosis, Portal Hypertension and Hepatic Decompensation in the Optum (A) and HealthCore (B) Databases

B. HealthCore

A. Optum

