The only approved drug therapy for PBC has been the bile acid ursodeoxycholic acid (UDCA), a physiological constituent of human bile (Lindor 2009). While UDCA therapy had a marked effect on the treatment of PBC, up to 40% of patients showed a suboptimal response or no response to UDCA (Corpechot 2008, Kumagi 2010). Such patients were at significantly increased risk of a poor clinical outcome due to PBC disease progression. Obeticholic acid (OCA) is a farnesoid X receptor (FXR) agonist and a modified bile acid that is derived from the primary bile acid chenodeoxycholic acid (CDCA), the natural human FXR ligand. OCA (Ocaliva[®]) has received marketing authorization in the US, the European Union (EU), and several other countries for the treatment of PBC in combination with UDCA in adults with an inadequate response to UDCA or as monotherapy in adults unable to tolerate UDCA. In the US, Ocaliva is contraindicated in patients with decompensated cirrhosis (eg, Child-Pugh Class B or C), a prior decompensation event, complete biliary obstruction, or compensated cirrhosis with evidence of portal hypertension. Approval in the US and the EU was based on a surrogate endpoint (reduction in ALP), and as part of regulatory commitments in these regions, the following postmarketing studies were initiated: Study 747-302, a Phase 3b/4 study designed to prospectively obtain evidence to confirm clinical benefit in PBC subjects, and Study 747-401, a Phase 4 study designed to evaluate the pharmacokinetics (PK) and safety of OCA in PBC subjects with hepatic impairment. Both 747-302 and 747-401 terminated early, due to the challenges of recruitment and long-term retention of patients with a rare disease subsequent to Ocaliva regulatory approval. Changes to endpoints and statistical analysis plans to accommodate low recruitment, low events rates, and early termination may necessitate the need for clinical trial data to be supplemented with real-world evidence, with the goal of providing regulators with a more complete evidence package characterizing the efficacy and safety of OCA in patients with PBC.

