As the probabilities used to construct the weights are not known, they will be estimated using a logistic regression model. The model will be fit using observed treatment as the outcome and main effect terms for each of the covariates. Covariates (assessed in the pre-index period) will include:

- Age at index date
- Sex
- Most recent liver biochemistry levels (TB, ALP, ALT, AST)
- Most recent platelet counts
- Time (in months) since UDCA failure
- Clinical evidence of portal hypertension (platelets <150,000 and/or non-bleeding varices)
- Cirrhosis
 - Komodo Health: cirrhosis diagnosis with liver imaging and/or biopsy within 6 months before diagnosis
 - Global PBC registry: biopsy stage 4, transient elastography ≥16.9 kPa, radiological evidence (nodular liver or enlargement of portal vein with splenomegaly), clinical features of portal hypertension defined as platelet count <140 000/mm³ with persistent decrease in serum albumin; or, TB >2x ULN, or prothrombin time/INR > ULN (not due to antithrombotic use)
- Most recent Charlson Comorbidity Index Score (Glasheen 2019)
- Insurance type at the index date (Komodo Health only: commercial, Medicare, Medicaid, dual eligible, other)

All diagnosis, procedure and laboratory codes used to define the control variables are listed in Appendix A.

Once the weights are constructed, a table of weighted SMDs between the groups will be constructed to assess balance. An absolute SMD of greater than 0.1 will indicate potentially problematic residual imbalance for the particular covariate. In the case that either the model-fitting algorithm fails to converge, or residual imbalance exists after weighting, the study team will attempt to reduce model complexity or reduce imbalances by implementing one or more of the following actions:

- Adding/removing interaction terms (1st order or higher)
- Using a spline for continuous variables
- Shrinking all coefficients in the model using a penalty

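### Komodo (747-405): coded cirrhosis without imaging or biopsy in the preceding 6 months is pooled with no cirrhosis code; this can leave residual confounding of modest size and unknown direction

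*Combined protocol and SAP*

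**What the plan says.** Section 10.1.1 lists cirrhosis among the covariates of the treatment model behind the SMR weights. For Komodo it is a "cirrhosis diagnosis with liver imaging and/or biopsy within 6 months before diagnosis". Section 12.4.5 gives the same rule with its codes: "cirrhosis ICD-10 (K74.5; K74.60; K74.69) with liver imaging and/or biopsy in 6 months preceding diagnosis". Neither section credits a code on its own, or imaging that follows the code. Neither says whether the diagnosis meant is the first cirrhosis code or any cirrhosis code.

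The flag has three uses. It is a weighting covariate (10.1.1) and it defines a subgroup (10.8). It would also be expected among the baseline covariates of the Cox model, although 10.2 does not list them. A related covariate needs no imaging claim: "Clinical evidence of portal hypertension (platelets <150,000 and/or non-bleeding varices" (10.1.1).

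Balance is judged on the covariates as measured: "An absolute SMD of greater than 0.1 will indicate potentially problematic residual imbalance for the particular covariate" (10.1.1). The support for the cirrhosis rule is aggregate: "Prevalence estimates in patients with PBC based on these codes in the HealthCore and Optum databases" were compared with the registry (12.4.5, Table 2). No sensitivity, no Komodo figure and no comparison by arm is given.

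**The concern.** The flag turns three groups into two. Patients with a code confirmed by prior imaging are cirrhotic. Patients with an unconfirmed code, and patients with no code, are both non-cirrhotic. Whether a coded patient is confirmed depends on the timing and frequency of imaging as well as on disease.

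SMR weighting makes the flag agree between arms. It makes true cirrhosis agree only if the unflagged groups contain the same share of missed cirrhosis. If they do not, the weighted arms differ on a prognostic factor while the weighted standardised mean difference for cirrhosis still looks good. The bias analysis in 10.9 is framed around unmeasured confounders and does not name misclassification of a measured one. The problem would therefore pass the planned checks unseen.

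**Working it through.** **The plan's own figures (Table 2).** All percentages reproduce from the counts. Compensated cirrhosis, with and without portal hypertension, is:

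- Registry: (314 + 105)/2,982 = 14.1%
- Optum: (271 + 276)/4,328 = 12.6%
- HealthCore: (225 + 295)/4,348 = 12.0%

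The claims-to-registry ratio is 12.0/14.1 = 0.85 to 12.6/14.1 = 0.89. The split differs more: without portal hypertension, 10.5% in the registry against 6.3% and 5.2% in claims. This is compatible with missed milder cirrhosis but does not prove it, because populations and definitions may differ.

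**Bias formula.** Let p1 and p0 be true cirrhosis prevalence in OCA and control indices, s1 and s0 the sensitivity of the flag, and k the hazard ratio for cirrhosis. Take specificity as 1 and let no other covariate correct the error.

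- Missed cirrhosis among unflagged controls: r = p0(1 − s0)/(1 − p0·s0)
- True cirrhosis in weighted controls: w = p1·s1 + (1 − p1·s1)·r
- Observed over true hazard ratio, approximately: (1 + (k − 1)p1)/(1 + (k − 1)w)

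Sensitivities by arm and k are not in the documents (Figure 3 is not shown). All values below are assumptions. The prevalences 14.1% and 15.6% come from Table 2; the latter is 419/2,694, compensated cirrhosis among compensated registry patients.

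**Mild difference.** p1 = p0 = 0.141, s1 = 0.90, s0 = 0.85. Then r = 0.02115/0.88015 = 0.0240 and w = 0.1269 + 0.8731 × 0.0240 = 0.1479. The factor is 1.282/1.2958 = 0.989 for k = 3 and 1.705/1.7395 = 0.980 for k = 6.

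**Strong difference.** p1 = p0 = 0.15, s1 = 0.9, s0 = 0.5, k = 4. Then r = 0.075/0.925 = 0.0811 and w = 0.135 + 0.865 × 0.0811 = 0.205. The factor is 1.45/1.615 = 0.898. Over prevalence 12 to 15%, k = 3 to 6 and s0 = 0.50 to 0.75, with s1 = 0.9, the range is 0.864 to 0.973.

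**Direction.**

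| p1 | p0 | s1 | s0 | k | Factor |
|---|---|---|---|---|---|
| 0.156 | 0.156 | equal | equal | any | 1.000 |
| 0.156 | 0.156 | 0.9 | 0.7 | 3 | 0.957 |
| 0.156 | 0.156 | 0.7 | 0.9 | 3 | 1.049 |
| 0.156 | 0.12 | 0.5 | 0.5 | 3 | 1.030 |
| 0.12 | 0.156 | 0.5 | 0.5 | 3 | 0.969 |

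Reversing the sensitivities reverses the sign. Equal sensitivity removes the bias only if true prevalence is also equal.

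**Effect of a separate level for unconfirmed codes.** Use the strong case again and assume every true cirrhosis is coded. If codes are also specific, levels 1 and 2 together hold all the cirrhosis and the factor is 1.000. Now let 5% of non-cirrhotic patients carry a false, unconfirmed code (0.85 × 0.05 = 0.0425). Level 2 is 0.015 + 0.0425 = 0.0575 of OCA indices. In controls it is 0.075 + 0.0425 = 0.1175, of which 0.075/0.1175 = 0.638 is true cirrhosis. Then w = 0.135 + 0.0575 × 0.638 = 0.172 and the factor is 1.45/1.515 = 0.957, against 0.898 for the binary flag. The same steps with 3% and 8% false codes give 0.970 and 0.944. With the sensitivities swapped, the binary flag gives 1.139 and three levels with 5% false codes give 1.101. The bias shrinks in both directions but is not removed.

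**The case against.** A reader might infer that scans ordered to work up OCA make confirmation more frequent in that arm, and so that the rule favours OCA. The documents give a possible motive, since section 4.1 says "Ocaliva is contraindicated in patients with decompensated cirrhosis" and extends this to compensated cirrhosis with evidence of portal hypertension. They do not support the inference:

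- Nothing states that imaging is part of an OCA work-up or that imaging rates differ by arm.
- If diagnosis means the first code, a later work-up scan cannot confirm cirrhosis that is already coded. If any code counts, a repeat code after a scan can confirm it in either arm. Work-up that uncovers new cirrhosis before a first code could raise OCA sensitivity, but that is also undocumented.
- Work-up that reveals portal hypertension may end in no OCA prescription. That patient can remain a control, now imaged, which pushes the other way.

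Other objections limit the size, and they stand. Section 12.4.5 ties the raised risk to cirrhosis with portal hypertension or decompensation; decompensation is excluded in both arms (7.3) and portal hypertension is a separate covariate. Platelets, bilirubin and portal hypertension would absorb part of any bias. A sensitivity of 50% sits poorly with Table 2: prevalences of 12.0 to 12.6% would then imply 24 to 25% true compensated cirrhosis, against 14.1% in the registry. Requiring imaging also protects specificity, which matters because K74.5 is an unspecified biliary cirrhosis code and may be used for PBC itself.

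The plan also has partial remedies. The formula in 10.9 takes confounder prevalence by arm and could be applied to missed cirrhosis, and the Clean Room Committee may change variable definitions while masked (10.11). But neither is directed at this flag, and the yes/no shell for cirrhosis by arm (Appendix B, Table 25) would not show unconfirmed codes.

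**Conclusion.** The point holds as a gap in the covariate, not as a demonstrated bias in favour of OCA. The pooling of unconfirmed codes with no code is explicit in two sections, and the balance check cannot detect its effect. Residual confounding arises if prevalence or confirmation differs by arm, and the documents do not allow the sign to be determined.

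The size is modest. Sensitivities near the Table 2 ratios (0.85 in controls, 0.90 in OCA) shift a null hazard ratio by 1 to 2%. A shift to 0.86 to 0.97 needs control sensitivity of 0.50 to 0.75 against 0.90 in OCA, a cirrhosis hazard ratio of 3 to 6, and no correction from the other covariates; these figures therefore lean large. The change is worth making because it is cheap, uses codes already listed, and does not depend on the direction.

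**What to change.** In the Komodo weight and outcome models, replace the binary flag with three levels built from claims up to the index date:

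1. cirrhosis code with imaging or biopsy within 6 months before or after it;
2. cirrhosis code without such imaging or biopsy;
3. no cirrhosis code.

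State whether diagnosis means the first code or any code. Show the Clean Room Committee the level-2 proportion by arm before the weights are finalised; this needs no outcome data. Keep the current binary flag as a sensitivity analysis.

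The cost is SAP wording and one extra parameter in each model; the codes are already in Appendix A. Level 2 may be small and will hold some false-positive codes, K74.5 being the obvious candidate. If it is too sparse to fit, use cirrhosis by code alone as a sensitivity analysis instead. The change does not recover cirrhosis that was never coded.
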